**\*\*\* Subject Population \*\*\***

**Subject Population(s) Checklist**

**Select All That Apply :**

- X Adults
- Cognitively Impaired Subjects
- Employees (specifically targeted)
- Fetuses
- Minors (under 18)
- Neonates
- Non English Speaking Subjects
- Pregnant Women
- Prisoners
- Students (specifically targeted)
- Terminally Ill Subjects
- Wards of the State
- Other (any population that is not specified above)

**Protocol Title:** Randomized trial of Propel stent vs Kenalog-soaked Nasopore after Frontal Drill-out

---

---

**\*\*\* Study Location \*\*\***

**Study Location(s) Checklist**

**Indicate where the study will be conducted. Select all that apply:**

- Saint Louis University, Medical Center Campus
  - Saint Louis University, Frost Campus
  - Saint Louis University, Madrid Campus
  - X Saint Louis University, SLUCare Practice Locations
  - SSM STL (DePaul Hospital, St. Mary's Health Center, St. Joseph (St. Charles, Wentzville, Lake Saint Louis), St. Clare)
  - Cardinal Glennon Children's Medical Center
  - X Saint Louis University Hospital (SSM Health- SLU Hospital)
  - SLU-SSM Cancer Center Research Alliance Sites
  - Other (In the box below, list any off-campus institutions or locations and describe the activities being conducted there. Please provide letters of cooperation and/or IRB approvals from each location to document support/approval of the study. You may provide such documentation as it becomes available, but you may not begin work at those sites until documentation of support is provided to the IRB.) Please refer to the Guidance for involving non-SLU institutions in human subject research.
- 

**\*\*\* General Checklist \*\*\***

**General Checklist**

**Select All That Apply :**

- Collection of Specimens
- Data collection via e-mail or the Internet
- Deception/Incomplete Disclosure
- Dietary Supplements, Vitamins, and Other Food Agents
- X FDA Approved Device
- X FDA approved drugs, reagents, other chemicals administered to subjects (even if they are not being studied), or biologic products
- Genetic Testing
- HIV Testing
- Human blood, cells, tissues, or body fluids
- International Research or Research on International Populations
- Investigational drugs, reagents, chemicals, or biologic products
- Investigational Device
- X Investigator Initiated Study \*?HELP?\*
- X Medical Records
- Photography, Video, or Voice-Recording Subjects
- X Questionnaires and/or tests

**Protocol Title:** Randomized trial of Propel stent vs Kenalog-soaked Nasopore after Frontal Drill-out

---

Radioisotopes/radiation-producing machines, even if standard of care  
rDNA/Gene Transfer Therapy

Registry(ies)

Specimens to be stored for future research projects (must be in consent form)

Study of existing data or specimens

X University Indemnified Study (SLU is responsible for liability coverage) \*?HELP?\*

Other (clarify in text box to the right)

Single Use. Provide a brief summary and justification for the Single Use Therapy. Note: This application will refer to research. For Single Use applications it is understood that 'research' will mean 'therapy'.

---

**\*\*\* Funding \*\*\***

**Funding Checklist**

X NONE

Funding - Grants/Contracts

Funding - Industry Sponsor

**NOTE:** Applicable grant application, contract or subcontract, investigator's brochure, and sponsor's protocol (for all industry sponsored clinical trials) must be attached. You will be prompted for these in section #16 (Attachments).

---

**\*\*\* Expedited Paragraphs \*\*\***

To request an Expedited Review, check the appropriate category(ies) below. Provide justification for your request for Expedited Review.

To qualify for expedited review, research activities must (1) present no more than minimal risk to human subjects, and (2) involve only procedures listed in one or more of the categories below.

**Protocol Title:** Randomized trial of Propel stent vs Kenalog-soaked Nasopore after Frontal Drill-out

---

1. Clinical studies of drugs and medical devices only when condition (a) or (b) is met.
  - a) **Research on drugs for which an investigational new drug application (21 CFR Part 31, 32) is not required. (Note: Research on marketed drugs that significantly increases the risks or decreases the acceptability of the risks associated with the use of the product is not eligible for expedited review.)**
  - b) **Research on medical devices for which**
    - (i) An investigational device exemption application (21 CFR Part 812) is not required; or
    - (ii) **The medical device is cleared/approved for marketing and the medical device is being used in accordance with its cleared/approved labeling.**
2. Collection of blood samples by finger stick, heel stick, ear stick, or venipuncture as follows:
  - a) **From healthy, nonpregnant adults who weigh at least 110 pounds. For these subjects, the amounts drawn may not exceed 550 ml in an 8-week period and collection may not occur more frequently than 2 times per week; or**

**From other adults and children, considering the age, weight, and health of the subjects, the collection procedure, the amount of blood to be collected, and the frequency with which it will be collected. For these subjects, the amount drawn may not exceed the lesser of 50 ml or 3 ml per kg in an 8-week period and collection may not occur more frequently than 2 times per week.**

Children are "persons who have not attained the legal age for consent to treatments or procedures involved in the research, under the applicable law of the jurisdiction in which the research will be conducted."

3. Prospective collection of biological specimens for research purposes by non-invasive means.

**EXAMPLES: (a) hair and nail clippings in a nondisfiguring manner; (b) deciduous teeth at time of exfoliation or if routine patient care indicates a need for extraction; (c) permanent teeth if routine patient care indicates a need for extraction; (d) excreta and external secretions (including sweat); (e) uncannulated saliva collected either in an unstimulated fashion or stimulated by chewing gumbase or wax or by applying a dilute citric solution to the tongue; (f) placenta removed at delivery; (g) amniotic fluid obtained at the time of rupture of the membrane prior to or during labor; (h) supra-and subgingival dental plaque and calculus, provided the collection procedure is not more invasive than routine prophylactic scaling of the teeth and the process is accomplished in accordance with accepted prophylactic techniques; (i) mucosal and skin cells collected by buccal scraping or swab, skin swab, or mouth washings; (j) sputum collected after saline mist nebulization.**

4. Collection of data through non-invasive procedures (not involving general anesthesia or sedation) routinely employed in clinical practice, excluding procedures involving X-rays or microwaves. Where medical devices are employed, they must be cleared/approved for marketing. (Studies intended to evaluate the safety and effectiveness of the medical device are not generally eligible for expedited review, including studies of cleared medical devices for new indications.)

**EXAMPLES: (a) physical sensors that are applied either to the surface of the body or at a distance and do not**

**Protocol Title:** Randomized trial of Propel stent vs Kenalog-soaked Nasopore after Frontal Drill-out

---

involve input of significant amounts of energy into the subject or an invasion of the subjects' privacy; (b) weighing or testing sensory acuity; (c) magnetic resonance imaging; (d) electrocardiography, electroencephalography, thermography, detection of naturally occurring radioactivity, electroretinography, ultrasound, diagnostic infrared imaging, doppler blood flow, and echocardiology; (e) moderate exercise, muscular strength testing, body composition assessment, and flexibility testing where appropriate given the age, weight and health of the individual.

5. Research involving materials (data, documents, records, or specimens) that have been collected, or will be collected solely for nonresearch purposes (such as medical treatment or diagnosis). (NOTE: Some research in this category may be exempt from the HHS regulations for the protection of human subjects. 45CFR 46.101(b)(4). This listing refers only to research that is not exempt.)
6. Collection of data from voice, video, digital, or image recordings made for research purposes.
7. Research on individual or group characteristics or behavior (including, but not limited to, research on perception, cognition, motivation, identity, language, communication, cultural beliefs or practices, and social behavior) or research employing survey, interview, oral history, focus group, program evaluation, human factors evaluation, or quality assurance methodologies. (NOTE: Some research in this category may be exempt from the HHS regulations for the protection of human subjects. 45 CFR 46.101(b)(2) and (b)(3). This listing refers only to research that is not exempt.)
8. [FOR IRB use only]. Continuing review of research previously approved by a convened IRB only when condition (a), (b), or (c) is met.
  - a) Previously approved research where
    - (i) The research is permanently closed to the enrollment of new subjects;
    - (ii) All subjects have completed all research-related interventions; and
    - (iii) The research remains active only for the long term follow-up of subjects.
  - b) Previously approved research where no subjects have been enrolled and no additional risks have been identified.
  - c) Previously approved research where the remaining research activities are limited to data analysis.
9. [FOR IRB use only]. Continuing review or research not conducted under an investigational new drug application or investigational drug exemption where expedited categories two (2) through eight (8) do not apply but the IRB has determined and documented at a convened meeting that the research involves no greater than minimal risk and no additional risks have been identified.

---

**\*\*\* Background, Purpose, Study Procedures \*\*\***

**Title**

Randomized trial of Propel stent vs Kenalog-soaked Nasopore after Frontal Drill-out
---

**Protocol Title:** Randomized trial of Propel stent vs Kenalog-soaked Nasopore after Frontal Drill-out

---

Complete Sections 1 - 16. In sections that allow reference to sponsor protocol or grant, clearly state section and page numbers. Any information that is different or specific to the local site should be in the SLU application. Specify N/A as appropriate.

## 1. Background

Page numbers from a sponsor's protocol/grant may be referenced in 1a and 1b.

- a) **Provide an introduction and background information. Describe past experimental and/or clinical findings leading to the formulation of the study, if applicable. Investigator Initiated studies must cite references in the response provided or attach a bibliography. \*?HELP?\***

Endoscopic sinus surgery is commonly used to manage chronic inflammatory frontal sinus disease that is not adequately controlled with medical therapy alone. In recalcitrant cases, a more extensive procedure called the modified endoscopic Lothrop procedure or frontal drill-out (FDO) procedure is often performed [1, 2]. The frontal drill-out procedure is performed endoscopically and its goal is to create one large common cavity between the left and right frontal sinuses and nasal cavities to allow adequate drainage and communication for subsequent drug delivery through sinonasal irrigations if indicated.[3, 4] Failure of this procedure is most commonly the results of re-stenosis of the outflow tract due to scarring, adhesions, or progressive disease such as polyposis.[5, 6] One meta analysis assessing the long-term complications of frontal drillouts reported an overall failure rate to be 13.9%, defined as those individuals needing further surgery.[2] Another clinical trial reported a failure rate for a 200-person study to be 30%.[7]

Placing a steroid-eluting biodegradable stent into the sinonasal cavities after surgery is thought to reduce the occurrence of re-stenosis, both by physically stenting the opening and by treating resultant inflammation with corticosteroid.[8] Propel stents are made of synthetic dissolvable polymer that contains a corticosteroid (mometasone furoate) and has been FDA-approved to stent and reduce inflammation over 30 days. Similarly, Nasopore is an FDA-approved fragmentable nasal dressing that is used as a stent. Kenalog soaking the Nasopore is thought to act as the functional equivalent of the mometasone furoate found in the Propel stent, but this use is investigational. The effect of stenting and its consequences on the outcomes of FDO specifically has also not been well studied.[8] Recent randomized-controlled trial of Propel stent placement after frontal sinusotomy (a less extensive form of frontal sinus surgery compared to FDO procedure) showed improvement in outcomes compared to no stent placement and no major complications.[9] There are no known randomized-controlled trials to date of propel stent placement or Nasopore-soaked kenalog placement after FDO procedure. We wish, therefore, to perform a randomized trial to compare the efficacy and outcomes of Nasopore-soaked kenalog versus propel stenting.

5. Hunter B, Silva S, Youngs R, Saeed A, Varadarajan V. Long-term stenting for chronic frontal

**Protocol Title:** Randomized trial of Propel stent vs Kenalog-soaked Nasopore after Frontal Drill-out

---

**Please save frequently**

- b) **Describe any animal experimentation and findings leading to the formulation of the study, if there is no supporting human data.**

N/A

## 2. Purpose of the study

- a) **Provide a brief lay summary of the project in <200 words. The lay summary should be readily understandable to the general public.**

Surgery on the frontal sinus is done for patients who have sinus problems that do not respond to medications. It involves making an opening within the right and left frontal sinus of the nose to help it drain. For severe frontal sinus disease the sinus is widely opened and the left and right sinuses become one large sinus. This is done with sharp instruments and rigid endoscopes placed through the nostrils. While the sinus heals after surgery, a stent or steroids or both may be used to try to help make sure that the opening does not close back up. Two current options for this are Propel stents and steroid-soaked Nasopore. Propel stents are FDA-approved. Nasopore and kenalog injection are both FDA-approved, but their use together is part of the study and not specifically FDA-approved. A previous study shows that Propel stents are useful to reduce scarring in other frontal sinus procedures. We would like to know whether this is true in larger frontal sinus surgery where one common cavity is made and whether both steroid-containing stents are the same.

Page numbers from a sponsor's protocol/grant may be referenced in 2b and 2c.

- b) **List your research objectives (specific aims & hypotheses of the study).**

Aim 1: To compare the difference in mean post-operative SNOT-22 scores between the Propel stent and Nasopore groups.

Aim 2: To compare the incidence of other surgical postoperative complications (diagnosed post-operative CSF leak, epistaxis requiring treatment, adhesions) between Propel stent and Nasopore.

Aim 3: To ascertain the incidence of surgical complications based on the specific frontal sinus

**Protocol Title:** Randomized trial of Propel stent vs Kenalog-soaked Nasopore after Frontal Drill-out

---

pathology

Hypothesis: Patients in the Kenalog-soaked Nasopore group will have outcomes that are non-inferior compared to the Propel stent group when comparing the long term symptom control as measured by SNOT-22 scores at 24 months follow-up.

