**Please save frequently**

- c) **Describe the study design (e.g., single/double blind, parallel, crossover, control, experimental, observational, etc.). If the study is investigator-initiated, a timeline for individual subject recruitment, follow-up, and analysis for the study is required. Also, indicate if the subjects will be randomized.**

Single blind (Subject) randomized, active control study. Subjects will be randomized 1:1 using the rand function in Microsoft Excel program.

Timeline: There will be a 2 year recruitment period during which patients will be recruited and eligible to participate. Eligible patients are those with chronic inflammatory sinonasal disease for whom frontal drill out procedure is indicated after evaluation by otolaryngologist. Patients eligible for the study and consenting to participate will be randomly assigned to one of two treatment groups: 1) Nasopore group will receive frontal drill out procedure as indicated with Kenalog-soaked Nasopore stent applied to the post-operative outflow tract and 2) Propel stent group will receive frontal drill out procedure as indicated followed by Propel stent placement applied to the post-operative outflow tract.

After the surgery, we will ask patients to follow up 5 times: post-operatively once between week 1-2, once between week 6-8, month 6, month 12, and month 24. All visits are standard of care.

During those visits, patients will fill out a short research related questionnaire that will ask about whether or not their symptoms have improved after surgery. We will also assess sinus cavities with rigid nasal endoscopy. Surgical complications will be documented and SNOT-22 scores will be determined by patients filling out SNOT-22 questionnaire at each visit.

Preliminary analysis will be performed once 5 patients have been enrolled and then every 6 months thereafter until 2 years of follow up of the last subject. We expect enrollment to occur over a period of 2 years.

- d) **If subjects will be given placebo, please justify placebo use. \*?HELP?\***

N/A

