Note that to maintain uniformity in care, post-operative antibiotics (defined as up to day 60 post-op) will only be given to patients in any group if frank purulence is noted intra-operatively. In addition, in accordance with other trials involving drug eluting stents [1], oral and topic steroids will not be given to patients in any group until 60 days post-operatively. Because oral steroids and certain antibiotics have anti-inflammatory properties, this could confound the result of the study. For this reason, we wish to avoid using them in a random fashion.

- c) **If the proposed study is a clinical trial where a drug, vaccine, device or other treatment is compared to a placebo group or comparison treatment group, what are the guidelines or endpoints by which early decisions regarding efficacy or lack of efficacy can be made? For example, it may be reasonable to stop enrollment on a study when efficacy has already been clearly demonstrated, to avoid unnecessary enrollments of additional subjects. Alternatively, it may be reasonable to stop enrollment when it is clear that efficacy will never be demonstrated, given the statistical power of the study as designed. Describe the guidelines that are in place to assist in making these determinations, if relevant to the proposed study.**

A difference in mean post-operative SNOT-22 score of 9 points will be considered a clinically significant difference. [1]

As such, preliminary analyses will be performed once 5 patients have been enrolled and then every 6 months thereafter until 2 years of follow up of the last subject. If clear statistically significant inferiority or superiority is demonstrated, the trial will be stopped.

[1] Chowdhury NI, Mace JC, Bodner TE, et al. Investigating the minimal clinically important

**Protocol Title:** Randomized trial of Propel stent vs Kenalog-soaked Nasopore after Frontal Drill-out

difference for SNOT-22 symptom domains in surgically managed chronic rhinosinusitis. Int Forum Allergy Rhinol. 2017;7(12):1149-1155.

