- d) **Describe how data analysis will be performed (statistical tests, methods of evaluating data) and indicate the smallest group/unit for which separate reporting will occur. For studies involving a questionnaire, if data and reliability information are available, please describe or provide references. For full board, unfunded studies describe sample size determination and power analysis. If none, please justify.**

The SNOT-22 score assesses symptomatic improvement and burden for patients with rhinosinusitis and is a clinically validated measure with high internal validity, correlation to its impact on quality of life, and longitudinal stability after sinus surgery. The minimal clinically important difference (MCID) for SNOT-22 is 9 points. [1, 2, 3, 4,5] From historical SLU otolaryngology practice data, patients who present to the otolaryngology clinic undergoing sinonasal surgery have a mean SNOT-22 score of  $42.0 \pm 8.0$ .

For this randomized, active control study of two types of sinonasal stents with steroid, we are interested in determining whether the cheaper and more available alternative (Nasopore and Kenalog) is similar to an accepted treatment (Propel stent) in symptom control at 24 months as measured by post-operative SNOT-22 scores.

For our sample size determination, we explore the lower limit of a 95% confidence interval (CI) around the mean difference between post-operative SNOT-22 scores of the two groups. We'll define the lower limit of the CI, or the margin of inferiority, as -8, which does not include the predetermined MCID of -9.  
We set power = 0.8 and alpha = 0.05.

Given: # subjects in each group =  $n = [(2(SD)^2) * (z_{1-(\alpha/2)} + z_{1-B})^2] / [(u_1 - u_2)^2]$  [ref 6]  
SD = 8.0, from SLU historical data  
 $[(z_{1-(\alpha/2)} + z_{1-B})]^2 = 7.8$ , estimated from z-tables,  $\alpha = 0.05$  and  $B = 0.2$

IF  $u_1 - u_2 = -8$  then  $n = 16$  subjects

To be conservative in our sample size calculation, we'll use  $u_1 - u_2 = -5$ , which yields a sample size of 40.

If we assume attrition rate of 10%, we estimate we'll need 45 subjects per group and a total of 90 subjects.

Difference in rates of complications will also be determined by chi-square testing for equality of proportions between groups. As these outcomes are expected to be few, our target sample size may not be adequate to determine statistical significance of differences. Reporting these complication rates nonetheless informs clinical practice.

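### The pre-operative SNOT-22 is collected but has no part in the between-arm comparison; prespecifying adjustment for it would probably narrow the interval at almost no cost

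*Combined protocol and SAP*

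**What the plan says.** Section 2b states "Aim 1: To compare the difference in mean post-operative SNOT-22 scores between the Propel stent and Nasopore groups", with a hypothesis of non-inferiority for Nasopore at 24 months. Section 3c uses the same quantity: "A difference in mean post-operative SNOT-22 score of 9 points will be considered a clinically significant difference". Section 3d begins its sizing with "For our sample size determination, we explore the lower limit of a 95% confidence interval (CI) around the mean difference between post-operative SNOT-22 scores" and sets "the margin of inferiority, as -8, which does not include the predetermined MCID of -9". The sizing formula is the ordinary two-sample one, with a raw SD of 8.0 and no covariate or correlation term. The SD is historical: "patients who present to the otolaryngology clinic undergoing sinonasal surgery have a mean SNOT-22 score of" 42.0 ± 8.0. No SD at 24 months is given.

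The only test that section 3d names is for complications: "Difference in rates of complications will also be determined by chi-square testing for equality of proportions between groups". No model is named for SNOT-22.

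The pre-operative score itself is available. Section 3b obtains it as standard of care to describe symptom burden, and section 3f says the questionnaire is routine at every visit. Section 8k places pre-operative data collection at consent, and section 3b randomizes after consent. No section uses the score as a covariate, in a change score or as a stratification factor.

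**The concern.** Non-inferiority here is judged on a confidence limit, so the width of the interval bears directly on the conclusion. A baseline value of the outcome, measured before randomization, is usually the most useful covariate a trial has. Here it is already collected but has no stated use in the comparison.

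The point is precision, not bias. Under randomization the unadjusted difference is unbiased, and its 95% interval has nominal coverage at a single final analysis. The repeated looks with a stopping rule (section 2c: "Preliminary analysis will be performed once 5 patients have been enrolled and then every 6 months thereafter"; section 3c: "If clear statistically significant inferiority or superiority is demonstrated, the trial will be stopped") are a separate matter, and nothing here vouches for them. They do make timing relevant: if the SNOT-22 model is not fixed before the first look, the choice between an adjusted and an unadjusted comparison could be made after seeing data.

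**Working it through.** **Inputs from section 3d.** SD 8.0; alpha 0.05, used two-sided; power 0.80; margin 8; difference used for the final sample size 5; attrition 10%.

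**Assumptions, not in the documents.** The correlation r between pre-operative and 24-month SNOT-22, shown from 0 to 0.6; 24-month SDs of 12 and 16 as alternatives to 8. All results are for one final analysis with 40 evaluable patients per arm.

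**The plan's own figure.** n per arm = 2 × SD² × 7.8 / difference².
- Difference 8: 2 × 64 × 7.8 / 64 = 15.6, so 16.
- Difference 5: 2 × 64 × 7.8 / 25 = 39.94, so 40. With the unrounded constant 7.849 it is 40.19, so 41.
- Attrition: 40 / 0.90 = 44.4, so 45 per arm and 90 in total.

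These agree with the plan and contain no baseline term.

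**Unadjusted half-width.** t(0.975; 78 df) × SD × √(2/n) = 1.991 × 8 × √(2/40) = 1.991 × 1.789 = 3.56.

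**Adjusted half-width.** The residual SD is SD × √(1 − r²), with 77 df. Estimating the covariate effect adds an expected 1/(80 − 4) = 1/76 = 1.3% to the variance. At r = 0.6: 1.991 × (8 × 0.8) × √(2/40) × √1.0132 = 2.87.

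**Break-even.** (1 − r²) × 1.0132 = 1 gives r = √(1 − 1/1.0132) = 0.114.

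Results at SD 8, with power from the noncentral t distribution:

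| | Variance change | Half-width | Power, 5-point difference | NI power, margin 8, true deficit 2 | NI power, margin 8, no true difference |
|---|---|---|---|---|---|
| Unadjusted | – | 3.56 | 78.8% | 91.2% | 99.3% |
| r = 0 | +1.3% | 3.59 | 78.3% | 90.8% | 99.2% |
| r = 0.1 | +0.3% | 3.57 | 78.7% | 91.1% | 99.3% |
| r = 0.2 | −2.7% | 3.51 | 79.9% | 91.9% | 99.4% |
| r = 0.3 | −7.8% | 3.42 | 82.0% | 93.2% | 99.6% |
| r = 0.5 | −24.0% | 3.11 | 88.6% | 96.7% | 99.9% |
| r = 0.6 | −35.2% | 2.87 | 92.9% | 98.4% | 99.98% |

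The 5-point column is also the non-inferiority power against 8 with a true deficit of 3, since 8 − 3 = 5.

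Non-inferiority power with margin 8 and no true difference, if the 24-month SD is larger than planned:

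| SD | Unadjusted | r = 0 | r = 0.2 | r = 0.5 | r = 0.6 |
|---|---|---|---|---|---|
| 12 | 83.8% | 83.3% | 84.7% | 92.2% | 95.5% |
| 16 | 59.8% | 59.3% | 61.0% | 71.7% | 78.3% |

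**Simulation.** With 40,000 trials per setting, no interim looks and the lower limit compared with −8, simulated power agreed with these figures. At SD 8 and a true deficit of 3, the unadjusted power was 0.789 to 0.791; the adjusted power was 0.785, 0.800 and 0.930 at r = 0, 0.2 and 0.6. Coverage of both intervals was 0.948 to 0.951. At SD 8 the adjusted interval was the narrower one in 20% of trials at r = 0, 35% at r = 0.1, 66% at r = 0.2 and over 99.9% at r = 0.6.

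**Why a covariate and not a change score.** A change score has SD × √(2(1 − r)). At r = 0.3 this is 8 × √1.4 = 9.47, worse than the 8.0 of the post-operative score alone. It improves on that score only when r exceeds 0.5.

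**The case against.** The strongest reply is that nothing is broken. The unadjusted comparison is valid, the sample size stands without adjustment, and on the plan's own inputs power is 99.3% before adjustment and between 99.2% and 99.98% after it. The larger gains need a true deficit, a larger 24-month SD or a correlation that the documents do not supply; at r = 0.2 the interval narrows by only about 1%. All of this stands. It is why the point is graded as an improvement and the gain is called likely, not certain.

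A two-sample formula does not rule out a later ANCOVA, because trials are often sized conservatively in this way. That is fair: section 3d names no SNOT-22 model at all, and the unadjusted reading is inferred from Aim 1 and the formula. The remedy is the same under either reading.

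Two smaller points also stand. Sections 8k and 3b place the pre-operative score at consent and randomization after consent, but neither says outright that the questionnaire is completed before allocation. And the 1.3% ceiling applies to the final analysis only. If the same model were used at early looks, the expected penalty at r = 0 would be 1/(N − 4): 1/16 = 6% with 20 patients in total and 1/6 = 17% with 10.

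**Conclusion.** The concern holds as a free improvement. The plan collects a pre-operative SNOT-22 and gives it no role in the SNOT-22 comparison. At the final analysis with 40 per arm, adjustment would change the half-width from 3.56 to somewhere between 3.59 (r = 0) and 2.87 (r = 0.6), with a gain for any r above about 0.11. The benefit is negligible if the SD is 8 and the arms are truly equal. It is useful if Nasopore is a few points worse (power 78.8% to 88.6% at a deficit of 3 and r = 0.5) or if the 24-month SD is larger (59.8% to 71.7% at SD 16 and r = 0.5). Confidence is high that the role is missing and that the cost is small; the size of the gain depends on an r that the documents do not give.

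**What to change.** In section 3d, before the first preliminary analysis at 5 patients:

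- Name the primary analysis as a linear model (ANCOVA) of 24-month SNOT-22 on treatment and pre-operative SNOT-22.
- Report the adjusted Propel-minus-Nasopore difference with its 95% CI, and conclude non-inferiority if the lower limit is above −8. Reading a higher score as more symptoms, this is the same as an upper limit below +8 for Nasopore minus Propel.
- State that the pre-operative questionnaire is completed before allocation, and whether the same model is used at the preliminary analyses.
- Give a rule for a missing pre-operative total, since section 9 (item 9) lets patients skip questions. One option is to substitute the mean over both arms, so that the patient stays in the analysis.
- Keep the unadjusted difference as a sensitivity analysis.

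The cost is a few sentences. No new data, visits or patients are needed, and the sample size can stay as it is. If the pre-operative score turned out to be uninformative, the expected loss at the final analysis would be at most 1.3% of variance.
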